# Table 2 Device Accountability Requirements

	Record	Subject Return	
10813115DOC	Version D	Page 47 of 118	Meanonic
10017115000	Varaian D	Daga 47 of 110	Medtronic

Device	Record on Site Received eCRF	Disbursement, Returned or Not Returned from Subject on Device Identification eCRF	Device to Investigational Center	Record Returned or Not Returned to Sponsor on Site Returned eCRF	Site Return Device to Sponsor at Conclusion of Study
MiniMed™ 780G Insulin Pump, (MMT-1884)	Yes	Yes	Yes	Yes	Yes
Guardian™ Sensor (3) (MMT-7020)	Yes	Yes	Yes (Unused only)	Yes	Yes (Unused only)
Guardian™ Sensor (4) (MMT-7040)	Yes	Yes	Yes (Unused only)	Yes	Yes (Unused only)
Guardian™ Link (3) Transmitter* (MMT-7811)	Yes	No	Yes	Yes	Yes
Guardian™ Link (3) Transmitter* (MMT-7911)	Yes	Yes	Yes	Yes	Yes
Guardian™ 4 Transmitter* (MMT-7841)	Yes	Yes	Yes	Yes	Yes
One-Press Serter (MMT-7512)*	No	No	No	No	No
Charger (MMT- 7715)*	No	No	No	No	No
Tester (MMT- 7736L)*	No	No	No	No	No
CONTOUR ® NEXT LINK 2.4 Study Meter (MMT-1352)	Yes	Yes	Yes	Yes	Dispose or return unused only

This document is electronically controlled *Medtronic Business Restricted* 056-F275, vB Clinical Investigation Plan Template

### **CIP321 Clinical Investigation Plan** Medtronic 10813115DOC Version D Page 48 of 118 Record Subject Return Disbursement, Device to **Returned or Not** Investigational **Record Returned** Record on **Site Return Device** Returned from Center or Not Returned to Site Received Device to Sponsor at Subject on Sponsor on Site eCRF Conclusion of Study Device Returned eCRF Identification eCRF Roche Accu-Chek™\* Guide Dispose or return Yes Yes Yes Yes unused only Link Study Meter (08116083022M) Precision Xtra™\* **Dispose or return** No No Yes No unused only Ketone Meter

\*Devices may be combined and distributed in kits.

The investigational center will promptly notify the sponsor of any device handling violation that might impact either the safety and/or welfare of subjects or data integrity.

# 6.8.1. Receipt and Inventory of Investigational Devices by Investigational Center

- Upon receipt of the study devices, investigational center staff take inventory of the shipment, making sure that information on the packing slips/invoices matches exactly the contents of the containers, as applicable, including:
  - Ship to Address
  - Reference Number
  - Device Type
  - o Quantity
  - Quantity per package
  - Lot number (where applicable)
  - Serial number (where applicable)
- Ensure that devices and supplies received have not reached or exceeded their expiration date
- Sign and date the packing slips/invoices, noting any discrepancies, and file in appropriate study binder
- Notify the study monitor of any discrepancies
- Enter the study device information on the appropriate eCRF in the study database.

10813115DOC

### 6.8.2. Storage of Study Devices at Investigational Center

Study devices are to be stored in a secure environment with access limited to authorized research personnel. Study devices are stored in the proper environmental conditions as identified in the IFU/labeling.

### 6.8.3. Disbursement of Study Devices

Each time a study device is disbursed to a subject by the investigator or authorized member of the research team, eCRF and/or source documentation will be completed as required. Documentation may include:

- Date of disbursement
- Subject ID
- Lot number(s)
- Serial Number
- Reference Number
- Amount dispensed

### 6.8.4. Return or Disposal of Study Devices

After use by the subject, the investigational center is expected to accept and retain all devices as described in Table 2 and store them in a secure environment. If containers/units/devices are missing, the reasons should be documented in the applicable eCRF. If discrepancies between the amounts used by subjects and the amounts expected to be returned exist, the reasons should be documented in the applicable eCRF.

Requirements for return of devices by subjects to the investigational center and return of device by the investigational center to the sponsor are listed in Table 2. The devices that are being returned to the investigational center may be returned to the sponsor as subjects complete the study, at the EOS visit or upon sponsor request.

Other unused consumable devices (i.e., infusion sets, alcohol wipes, study meter supplies, tape, etc.), supplies or materials may be returned to the sponsor, they may be retained by investigational centers for educational purposes only, or they may be disposed of properly by investigational center staff.

Disposable devices and supplies that have been *used* by a subject will be disposed of properly by the subject or the investigational center staff during the conduct of the study.

All study devices that are required to be entered into the study database must be accounted for as described above before they are returned to the sponsor.

10813115DOC

# 7. Selection of Subjects

# 7.1. Study Population

A total of up to 350 subjects will be enrolled at up to 30 investigational centers across the US in order to have 250 subjects who complete the study period. The number of subjects enrolled in the continued access period depends on the subjects' desire to continue.

Version D

# 7.2. Subject Enrollment

Subjects will be considered enrolled in the study upon signing the Informed Consent Form (ICF)/ Assent Form.

A subject will be assigned a unique study subject ID (SID) via the eCRF, which is a 9-digit code (321XXXXX). The first three numbers refer to the CIP number (321), the next three numbers refer to the investigational center number, and the last 3 numbers refer to the subject number assigned during Visit 1 (e.g., 321002001 is subject 001 from site 002).

The investigator will maintain a log of all subjects enrolled in the clinical study, assigning a SID linked to their names, alternative SID, and contact information.

# 7.3. Inclusion Criteria

# General Inclusion Criteria

- 1. Subject is age 7-75 years at time of Screening
- 2. Subjects 14-75 years of age: A clinical diagnosis of type 1 diabetes for 2 years or more as determined via medical record or source documentation by an individual qualified to make a medical diagnosis
- 3. Subjects 7-13 years of age: A clinical diagnosis of type 1 diabetes for 1 year or more as determined via medical record or source documentation by an individual qualified to make a medical diagnosis
- 4. Individual of legal age is capable of providing consent.

# Study-specific inclusion criteria

- 5. Subject is willing to perform  $\ge$  4 finger stick blood glucose measurements daily
- 6. Subject is willing to perform required sensor calibrations
- 7. Subject is willing to wear the system continuously throughout the study
- 8. Subject must have a minimum daily insulin requirement (Total Daily Dose) of greater than or equal to 8 units
- 9. Subject has a Glycosylated hemoglobin (HbA1c) less than 10% (as processed by Central Lab) at time of Screening visit

Page 50 of 118

10813115DOC

Version D

# Note: All HbA1c blood specimens will be sent to and tested by a NGSP certified Central Laboratory. HbA1c testing must follow National Glycohemoglobin Standardization Program (NGSP) standards.

- 10. Subject has TSH in the normal range OR if the TSH is out of normal reference range the Free T3 is below or within the lab's reference range and Free T4 is within the normal reference range.
- 11. Pump therapy for greater than 6 months prior to screening (with or without CGM experience)
- 12. Subject must have a companion or caregiver available at night for the duration of the study period who resides (or will live) in in the same building (or home). A companion or caregiver should also be available during exercise challenges in the same building, home or location (if not at home). This requirement may be verified by subject report at screening visit.
- 13. Subject willing to upload data from the study pump, must have Internet access and a computer system that meets the requirements for uploading the study pump
- 14. If subject has celiac disease, it has been adequately treated as determined by the investigator
- 15. Subject is willing to take one of the following insulins and can financially support the use of either of the 2 insulin preparations throughout the course of the study (i.e. co-payments for insulin with insurance or able to pay full amount)
  - Humalog™\* (insulin lispro injection)
  - NovoLog™\* (insulin aspart)
- 16. Subjects with history of cardiovascular event 1 year or more from the time of screening must have an EKG within 6 months prior to screening or during screening. If subject has an abnormal EKG, participation is allowed if there is clearance from a cardiologist
- 17. Subjects with the 3 or more cardiovascular risk factors listed below must have an EKG within 6 months prior to screening or during screening. If subject has an abnormal EKG, participation is allowed if there is clearance from a cardiologist
  - a. Cardiovascular risk factors include:
    - Age >35 years
    - Type 1 diabetes of >15 years' duration
    - Presence of any additional risk factor for coronary artery disease
    - Presence of microvascular disease (proliferative retinopathy or nephropathy, including microalbuminuria)
    - Presence of peripheral vascular disease
    - Presence of autonomic neuropathy
- 18. Subjects with history of cardiovascular event 1 year or more from the time of screening must have a stress test within 6 months prior to screening or during run in period. If subject fails stress test, participation is allowed if there is clearance from a cardiologist

# 7.4. Exclusion Criteria

- 1. Subject has a history of 1 or more episodes of severe hypoglycemia, which resulted in any the following during the 6 months prior to Screening:
  - a. Medical assistance (i.e. Paramedics, Emergency Room (ER) or Hospitalization)
  - b. Coma
  - c. Seizures
- 2. Subject has been hospitalized or has visited the ER in the 6 months prior to Screening resulting in a **primary diagnosis** of uncontrolled diabetes

# CIP321 Clinical Investigation Plan Page 52 of 118 Medtronic 10813115DOC Version D Page 52 of 118 Medtronic

- 3. Subject has had Diabetic Ketoacidosis (DKA) in the 6 months prior to Screening.
- 4. Subject has Hypoglycemia Unawareness, measured by the Gold questionnaire as ≥4 (Gold, MacLeod et al. 1994) at Screening
- 5. Subject is unable to tolerate tape adhesive in the area of sensor placement
- 6. Subject has any unresolved adverse skin condition in the area of sensor placement (e.g., psoriasis, dermatitis herpetiformis, rash, Staphylococcus infection)
- 7. Women of child-bearing potential who have a positive pregnancy test at Screening or plan to become pregnant during the course of the study
- 8. Females who are sexually active and able to conceive will be excluded if they are not using an effective method of contraception and do not agree to continue using an effective method of contraception for the duration of the study as determined by investigator.
- 9. Subject has had any of the following cardiovascular events within 1 year of screening: myocardial infarction, unstable angina, coronary artery bypass surgery, coronary artery stenting, transient ischemic attack, cerebrovascular accident, angina, congestive heart failure, ventricular rhythm disturbances or thromboembolic disease
- 10. Subject is being treated for hyperthyroidism at time of Screening
- 11. Subject has a diagnosis of adrenal insufficiency
- 12. Subject has taken any oral, injectable, or intravenous (IV) glucocorticoids within 8 weeks from time of Screening, or plans to take any oral, injectable, or IV glucocorticoids during the course of the study
- 13. Subject is actively participating in an investigational study (drug or device) wherein he/she has received treatment from an investigational study drug or investigational study device in the last 2 weeks
- 14. Subject is currently abusing illicit drugs
- 15. Subject is currently abusing marijuana
- 16. Subject is currently abusing prescription drugs
- 17. Subject is currently abusing alcohol
- 18. Subject is using pramlintide (Symlin), DPP-4 inhibitor, liraglutide (Victoza or other GLP-1 agonists), metformin, canagliflozin (Invokana or other SGLT2 inhibitors) at time of Screening
- 19. Subject has a history of visual impairment which would not allow subject to participate in the study and perform all study procedures safely, as determined by the investigator
- 20. Subject has elective surgery planned that requires general anesthesia during the course of the study
- 21. Subject has a sickle cell disease, hemoglobinopathy; or has received red blood cell transfusion or erythropoietin within 3 months prior to time of Screening
- 22. Subject plans to receive red blood cell transfusion or erythropoietin over the course of study participation
- 23. Subject diagnosed with current eating disorder such as anorexia or bulimia
- 24. Subject has been diagnosed with chronic kidney disease that results in chronic anemia
- 25. Subject has a hematocrit that is below the normal reference range of lab used.
- 26. Subject is on dialysis
- 27. Subject has serum creatinine of >2 mg/dL.
- 28. Research staff involved with the study.

10813115DOC

Version D

Page 53 of 118

# **8. Study Site Requirements**

# 8.1. Study Site Activation

During the activation process (prior to subject enrollment), Medtronic will train investigational center staff. If new members join the study investigational center team, they will receive training on the applicable study requirements relevant to their role before contributing to the study.

Prior to performing study related activities, all regulatory requirements shall be fulfilled.

# 9. Study Procedures

# 9.1. Overview

# **Run-In Period Synopsis (Run-In Visits 1-4)**

The purpose of the run-in period is to ensure that study subjects are introduced to study devices. There is a window of 45 days from the end of Visit 1 to the end of Visit 4 during which time subjects should complete run-in. Subjects will be started on the study pump (and CGM if applicable) at Visit 2.

# • Devices Worn:

- Study pump
- Guardian™ Sensor (3)
- Guardian™ Link (3) transmitter

10813115DOC

	Study Period Synopsis (Visits 5-18)					
Overview:						
The study period is approximately 90 days long.						
	Study Period Device Procedures					
• Devic	ces Worn:					
0	Study pump					
0	Guardian™ Sensor (3)					
0	Guardian™ Link (3) transmitter					
Calib	ration Requirements with Study Meter:					
0	Approximately 30 minutes to 2 hours after the Guardian ™ Sensor (3) is initialized, the study pump will alert the user to enter a SMBG to perform initial calibration.					
0	After the first calibration, the user must calibrate the Guardian ™ Sensor (3) with the study meter within 6 hours of the first calibration. BG values from the study meter, which have been confirmed by subjects, will be used for calibrations.					
0	The user must calibrate via SMBG with the study meter when prompted by the study pump. BG values from the study meter, which have been confirmed by subjects, will be used for calibrations.					
0	The user must calibrate with the study meter every 12 hours after last calibration.					
0	Minimum of one calibration every 12 hours will be required with the study meter					
0	Best practices should be followed for each BG measurement (e.g. clean hands, "second drop" technique and accepting the calibration on the pump without delay)					
0	Other recommendations:					
	
 
Should always have clean dry fingers when checking blood glucose
 
					
	
 
Only fingertips should be used to obtain blood samples for calibration
 
					
Auto	Mode Settings:					
0	The Auto Mode (Closed Loop) setpoint for the closed loop algorithm:					

Medtronic

Page 54 of 118

10813115DOC

	The sponsor will provide guidance on the starting setpoint for subjects based on cohorts listed below:
	
 
A minimum of 50 subjects 14 years of age and older will start the study with an Auto Basal setpoint of 100 mg/dL. They will switch to the 120 mg/dL setpoint after 45 days (± 5 days) of the study period.
 
A minimum of 50 subjects 14 years of age and older will
 

	start the study with an Auto Basal setpoint of 120 mg/dL. They will switch to the 100 mg/dL setpoint after 45 days (± 5 days) of the study period.
	
 
A minimum of 50 subjects 7-13 years of age will start the study with an Auto Basal setpoint of 100 mg/dL. They will switch to the 120 mg/dL setpoint after 45 days (± 5 days) of the study period.
 

	
 
A minimum of 50 subjects 7-13 years of age will start the study with an Auto Basal setpoint of 120 mg/dL. They will switch to the 100mg/dL setpoint after 45 days (± 5 days) of the study period
 

	The investigator has the discretion to start subjects at either the 100 mg/dL or 120 mg/dL setpoints, while the Sponsor will ensure that the required minima for each setpoint are being met. Regardless of which setpoint is being set at the beginning of the study period, subjects should attempt to change the setpoint after 45 days (+/- 5 days) of the study period. For example: A subject who starts at the 100 mg/dL setpoint, should attempt to change the setpoint to 120 mg/dL after 45 days.
	emp target setting in the pump may be used any time, e.g., when t exercises. Temp Target Threshold is set to 150 mg/dL.
•	During this time, subjects may use the temporary target of 150 mg/dL for one of the 3 days at each setpoint.
•	The Temp target may be used during exercise challenges per investigator discretion

 
Alerts
 
	that are fixed into the system:
•	SG at or below 50 mg/dL
•	When SG at or above 250 mg/dL for more than 3 hours

10813115DOC

Version	D

0 0 0 0	
 
sensor reading) is recommended to be set at 70 mg/dL
 
Alert setting options may be set per investigator discretion for subjects 14 years and older
 
Low Setup alert for subjects 7-13 years of age should not be set lower than 70 mg/dL
 
Insulin carbohydrate ratios may be adjusted throughout the study
 
Active insulin time may also be adjusted
 

0	SmartGuard ™ features other than Auto Mode (i.e. Suspend on Low and
	Suspend before Low) should be activated during times when subjects are not in Auto Mode during the study period
• Manu	al Mode Settings:
0	High Setup limit recommended to be set at 300 mg/dL
	
 
Alert setting options may be set per investigator discretion
 

0	
	
 
Alert setting options may be set per investigator discretion
 

	
 
Low Setup alert for subjects 7-13 years of age should not be set lower than 70 mg/dL
 

0	Predictive alerts and rate of change alerts are optional
0	Alerts that are fixed into the system:
	SG at or below 50 mg/dL
	When SG at or above 250 mg/dL for more than 3 hours
0	Consider setting the glucose target in the bolus wizard calculator, i.e. 120 mg/dL or higher, based on investigator discretion.
• Moni	toring Method:
0	CONTOUR®NEXT LINK 2.4 study meter

10813115DOC

Continued Access 780G System Use Synopsis
Overview:
Continued access visits will take place at 90 day ( $\pm$ 14 days) intervals from the last study period visit.
Study Period Device Procedures
Devices Worn:

 
780G Insulin pump
 

 
Guardian™ Sensor (4) or Guardian™ Sensor (3)
 

 
Guardian™ 4 transmitter or Guardian™ Link (3) transmitter
 

 
Calibration Requirements with Study Meter:         
 
Calibrations are not required
 
 
 

 
Every time a BG is entered, calibration occurs
 

 
Best practices should be followed for each BG measurement (e.g. clean hands, "second drop" technique and accepting the calibration on the pump without delay)
 

• Other recommendations:

 
Should always have clean dry fingers when checking blood glucose
 

 
Only fingertips should be used to obtain blood samples
 

Auto Mode Settings:

 
The automatic basal target and active insulin time should be set according to investigator discretion.
 

Manual Mode Settings:

 
High Setup limit recommended to be set at 300 mg/dL
 

 
Alert setting options may be set per investigator discretion
 

 
Low Setup limit recommended to be set at 70 mg/dL
 

 
Alert setting options may be set per investigator discretion
 

Monitoring Method:

 
Roche Accu-Chek™* Guide Link study meter
 

10813115DOC

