At the end of the study period, subjects will have the opportunity to continue using the AHCL system at home until the Sponsor receives FDA approval to commercialize the products and the system is commercially available. During the continued access period, subjects will be asked to use the system as intended and to upload device data on a weekly basis. See Visit Schedule tables for frequency of device uploading. Office visits will be required at 3 month intervals.
Continued Access Period expansion:
During the continued access period, all participating subjects will transition from the 670G system, version 4.0 AHCL, to the 780G system which features Bluetooth ® connectivity. The CGM used with 780G will be Guardian ™ 4 Transmitter with the Guardian ™ Sensor (4).
Subjects will continue to use the 780G system at home until the sponsor notifies sites to end subjects' study participation.
The MiniMed ™ Clinical App and the Medtronic CareLink ™ Clinical App will be used by subjects when they are available.
SMBG recommendations for 670G system, version 4.0 AHCL : Typically, one SMBG is required every 12 hours for calibration. Routine SMBG is not required. Occasionally, subjects may receive a notification if the pump needs a BG to enter or stay in Auto Mode. For study purposes, subjects will be instructed to perform SMBG if they are feeling low (but sensor glucose is not low) or high and if they are experiencing a severe hypoglycemic event, a severe hyperglycemic event or DKA.
SMBG recommendations for 780G system: With the 780G system and the Guardian ™ 4 transmitter, calibration is not required. However, a calibration is optional and will occur any time a BG is entered. Occasionally, subjects may receive a notification if the pump needs a BG to enter or stay in Auto Mode. For study purposes, subjects will be instructed to perform SMBG if they are feeling low (but sensor glucose is not low) or high including a severe hypoglycemic event, a severe hyperglycemic event or DKA.

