#### SMBG recommendations for 670G system, version 4.0 AHCL:

Typically, one SMBG is required every 12 hours for calibration. Routine SMBG is not required. Occasionally, subjects may receive a notification if the pump needs a BG to enter or stay in Auto Mode. For study purposes, subjects will be instructed to perform SMBG if they are feeling low (but sensor glucose is not low) or high and if they are experiencing a severe hypoglycemic event, a severe hyperglycemic event or DKA.

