#### SMBG recommendations for 780G system:

With the 780G system and the Guardian™ 4 transmitter, calibration is not required. However, a calibration is optional and will occur any time a BG is entered. Occasionally, subjects may receive a
CIP321 Clinical Investigation Plan			
10813115DOC	Version D	Page 37 of 118	Medtronic

notification if the pump needs a BG to enter or stay in Auto Mode. For study purposes, subjects will be instructed to perform SMBG if they are feeling low (but sensor glucose is not low) or high including a severe hypoglycemic event, a severe hyperglycemic event or DKA.

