# Figure 1. MiniMed™ 670G Insulin Pump, version 4.0 AHCL

# 6.3.2. MiniMed™ 780G Insulin Pump

The MiniMed™ 780G Insulin Pump houses electronics, a pumping mechanism, a user interface, and a medication reservoir within the same physical device. The pump communicates via Bluetooth® Low Energy wireless communication protocol with compatible devices in the MiniMed™ 780G System: Guardian™ 4 Transmitter (connected to Guardian™ Sensor [4]), Roche's Accu-Chek™\* Guide Link Blood Glucose Meter, consumer electronic devices with the MiniMed™ Clinical App, CareLink™ Clinical App with CareLink™ Personal software or Blue Adapter with CareLink™ Personal/CareLink™ system software.

The most notable enhancements to the MiniMed™ 780G System are the incorporation of modifications to the closed loop algorithm that includes the addition of adjustable target setpoints (100 mg/dL, 110 mg/dL and 120 mg/dL), an auto correction bolus without user input or acknowledgement and fine tuning of safeguards in order to reduce auto mode exits and improve the user experience.

The MiniMed™ 780G Pump interacts with the following devices:

- The MiniMed™ 780G Pump receives the sensor glucose values and sensor integrity check from the transmitter.
- The MiniMed™ 780G Pump receives blood glucose values from the Roche's Accu-Chek™\* Guide Link blood glucose meter
- In addition, the MiniMed™ 780G Pump transmits data to a compatible consumer electronic device with the MiniMed™ Clinical App, to provide a secondary display for passive monitoring of CGM and pump data for the user.
- The MiniMed™ 780G Pump also transmits data to CareLink™ Personal/CareLink system software through the Blue Adapter/ MiniMed™ Clinical App.

This document is electronically controlled *Medtronic Business Restricted* 056-F275, vB Clinical Investigation Plan Template

Page 40 of 118

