100 mg/dL or 120 mg/dL (depending on what is required at that time of the study period), unless a subject prefers to use the 150 mg/dL target before, during and immediately after the exercise challenges. For the remainder of days, the temporary target will be set at the Investigator's discretion. A log will be used to collect information about exercise type, date, time (start and finish of exercise), duration and name of the companion. The log should also contain confirmation that SMBG was done at the beginning of exercise, as well as 2 and 4 hours after the start of the exercise. The timing of the exercise challenge will be at the investigator's discretion. A photograph should be taken on each day of the exercise to indicate that exercise took place. Subjects may also use a Smart Phone application to document their exercise. The subject's companion must be physically present in the same building, home or location (if not at home) during the exercise challenge, must be able to check SMBG (in case it is needed) and give glucose/administer glucagon as needed. Examples of types of exercise include but are not limited to:

- Running
- Cycling
- Swimming
- Hiking
- Walking
- Games (e.g. Wii interactive video games)
- Indoor/outdoor playground (Pediatric subjects)
- Yoga/stretching
- Any sport activity which involves ongoing physical movement (i.e., tennis, golf, basketball, tee ball or volleyball)
- Dancing
- Zumba
- Aerobics
- Spinning

Continued Access period:

At the end of the study period, subjects will have the opportunity to continue using the AHCL system at home until the Sponsor receives FDA approval to commercialize the products and system is commercially available. During the continued access period, subjects will be asked to use the system as intended and to upload device data on a weekly basis. See Visit Schedule tables for frequency of device uploading. Office visits will be required at 3 month intervals.

Continued Access Period expansion:

During the continued access period, all participating subjects will transition from the 670G system, version 4.0 AHCL, to the 780G system which features Bluetooth® connectivity. The CGM used with 780G will be Guardian™ 4 Transmitter with the Guardian™ Sensor (4). Subjects will continue to use the 780G system at home until the sponsor notifies sites to end subjects' study participation. The MiniMed™ Clinical App and the Medtronic CareLink™ Clinical App will be used by subjects when they are available.

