SMBG recommendations:

Typically, one SMBG is required every 12 hours for calibration. Routine SMBG is not required. Occasionally, subjects may receive a notification if the pump needs a BG to enter or stay in Auto Mode. For study purposes, subjects will be instructed to perform SMBG if they are feeling low (but sensor glucose is not low) and if they are experiencing a severe hypoglycemic event, a severe hyperglycemic event or DKA.

Companions:

Subjects will be required to have a companion who resides (or will live) in the same building (or home) during the proposed study at night, and also to be physically present in the same building, home or location (if not at home) during the exercise and meal challenges. A companion should be present during meal challenges and for 4 hours following the start of the meal. Companions should be able to check SMBG (in case it is needed), give glucose or administer glucagon.

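### Protocol Section 9.1 waives calibration for every 780G set-up it lists, including the Guardian Link (3) transmitter, which works from meter calibration (minor; continued access only)

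*Protocol*

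**What the plan says.** The 780G synopsis box in Protocol Section 9.1 gives two transmitters (Guardian 4 or Guardian Link (3)) and two sensors (Sensor (4) or Sensor (3)) as devices worn. Under calibration it says "Calibrations are not required". The next line says that any entered BG acts as a calibration. That explains what an entry does; it does not restrict the waiver to one transmitter.

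Other places are narrower:

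- **Where the waiver is tied to a device.** The SMBG recommendations for the 780G, in the Synopsis and again in Section 5, concern the 780G together with the Guardian 4. The Synopsis reads "4 transmitter, calibration is not required. However, a calibration is optional and will occur any time a BG is entered"; Section 5 has the same "4 transmitter, calibration is not required".
- **Which CGM goes with the 780G.** The Synopsis and Section 5, under the continued access expansion, say "The CGM used with 780G will be Guardian" and go on to name the Guardian 4 Transmitter with Sensor (4). Section 6.3.2 lists as compatible the "4 Transmitter (connected to Guardian" Sensor (4). SAP Section 5 repeats the Guardian 4 and Sensor (4) sentence.
- **The calibration frequency.** Section 5 says "Typically, one SMBG is required every 12 hours for calibration", but under the 670G heading. The study-period box in Section 9.1 sets a minimum of one calibration every 12 hours for Sensor (3) with Link (3).

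**The concern.** Site staff are likely to take device instructions from Section 9.1. Read literally, it tells a 780G subject wearing Link (3) that no calibration is needed, although that transmitter relies on meter values to produce a glucose reading. Table 3 in Section 10.1 names sensor failure after a missed calibration as a route to both hypoglycemia and hyperglycemia under closed-loop therapy. Section 3.2 makes subject safety on the 780G a purpose of the continued access period, and the subjects include children aged 7 to 13. An incorrect calibration instruction there deserves correction even if few subjects, or none, are exposed to it.

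**Working it through.** The plan gives no statistical figure to reproduce here. The check is a comparison of texts, with one line of arithmetic.

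**1. Does Link (3) need calibration?** Section 6.4.2 says its calibration algorithm turns the sensor signal into a glucose value using meter readings relayed through the pump, so it does. Section 9.1, for the study period, requires an initial calibration, a second within 6 hours, and then at least one every 12 hours. Section 3.1 attributes calibration-free operation to the new algorithm in the Guardian 4 transmitter.

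**2. At what frequency?** One every 12 hours is 24 / 12 = 2 per day. Section 3.1 likewise says that the current algorithm needs at least two per day, though it does not name Link (3). The 780G box requires 0 per day for every set-up it lists. The minimum of 2 is documented for Link (3) with the 670G study pump; applying it to the 780G is an inference.

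**3. Which listed set-ups are affected?** Two transmitters and two sensors give 2 × 2 = 4 nominal combinations. Section 6.4.2 connects Link (3) to Sensor (3) in this study, so one described pairing is affected: Link (3) with Sensor (3). The waiver is not in question for the Guardian 4.

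**4. Is the rule supplied elsewhere for Link (3) on the 780G?**

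| Place | What it gives | Covers Link (3) on the 780G? |
|---|---|---|
| Synopsis and Section 5, SMBG for the 670G | 12-hour calibration | No, 670G only |
| Section 9.1, study period | 12-hour minimum | No, study period only |
| Synopsis and Section 5, SMBG for the 780G | Waiver with Guardian 4 | No, silent on Link (3) |
| Section 9.8.3 | Sensor glucose is calibrated with the study meter | No frequency given |
| SAP Section 5, SMBG | "Typically, one SMBG is required every 12 hours for calibration. Routine SMBG is not required", not split by pump | General, but a SAP is not a site instruction |

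The labeling and IFUs (Section 18.2) and the Visit Details Table (Section 18.4) are separate documents and were not available for this check.

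**5. Is Link (3) intended with the 780G?** The documents do not settle it. Against: the Synopsis, Section 5, Section 6.3.2 and the SAP name only Guardian 4 with Sensor (4). For: 9.1 lists it outright, Section 3.1 treats the new transmitter as something the 780G might include, Section 6.4.2 gives Link (3) a Bluetooth Low Energy option, and Section 6.4.9 describes the meter used with the 780G as supporting calibration of Sensor (3) or Sensor (4).

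**6. Does either answer make 9.1 right?** No. If Link (3) is not intended, the calibration line is correct but the device list is wrong. If it is intended, the device list is correct, the calibration line is wrong for that pairing, and the Synopsis, Section 5 and Section 6.3.2 are incomplete.

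**The case against.** The best counter-argument is that the pairing cannot arise. The Synopsis, Section 5 and the SAP move all participating subjects to the 780G with Guardian 4 and Sensor (4), and Section 6.3.2 omits Link (3). On those texts the waiver is correct for everyone and 9.1 merely carries a stray item in its device list. This may be so, but it moves the error to the device list without removing it.

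The second argument is that harm is unlikely even if the pairing is used. Link (3) prompts for calibration (Section 6.4.2), and the pump may ask for a BG to enter or stay in Auto Mode (Section 5). Section 9.7.3 promises training on calibration. Table 3 in Section 10.1 directs users to the user guides, provides transmitter training, and bars treatment decisions without sensor values until a BG is confirmed. Section 9.3 adds training at the 780G start and CareLink review on days 1, 3 and 7. All of this stands, and it keeps the risk small. It does not correct the instruction.

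The third argument is that 0 against 2 calibrations per day overstates what is known, because no visible protocol text sets the 12-hour rule for Link (3) on the 780G, and Section 6.4.2 describes prompting when needed in place of a strict timetable. This also stands. The need for meter calibration is documented; its frequency on the 780G is for the sponsor to confirm.

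**Conclusion.** The point holds as a minor error in a safety instruction, confined to the continued access period. For one listed pairing, Link (3) with Sensor (3), the waiver in Section 9.1 conflicts with how the protocol says the transmitter works. The number of subjects given that pairing is not stated and may be zero.

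A reader might infer more, and the documents do not support it:

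- That 780G subjects will be left on uncalibrated sensors. The prompts, training and user guides work against this, and the pairing may never be dispensed.
- That the trial's results are affected. Continued access has descriptive and safety summaries only; the study-period hypotheses and their sample sizes concern the 670G version 4.0 system.
- That Link (3) in 9.1 is plainly deliberate, or plainly a leftover. The current text points both ways, and the version history describes superseded text and was not used to decide it.

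The conclusion assumes that Section 6.4.2 describes Link (3) accurately whichever pump it is used with. It also assumes that the documents not seen do not already settle the matter for sites; if they do, 9.1 should still agree with them.

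**What to change.** The sponsor should first confirm which CGM devices may be used with the 780G, and then make one of two edits to Section 9.1:

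- **If Sensor (3) and Link (3) are not intended:** delete them from the 780G device list. The waiver can then stay as it is. Check that Sections 3.1 and 6.4.9 of the protocol, and the matching background text in SAP Section 3.1, do not still suggest otherwise.
- **If they are intended:** limit the waiver to the Guardian 4 transmitter and state that Link (3) with Sensor (3) must be calibrated with the study meter. Give the frequency only after confirming that the study-period minimum of one every 12 hours applies on the 780G. Align the Synopsis, Section 5 and Section 6.3.2. The CGM sentence in SAP Section 5 should be brought into line for consistency.

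The change is wording only: one protocol section in the first case, four (Synopsis, 5, 6.3.2 and 9.1) plus the SAP in the second. It still goes through Section 16.7: IRB notification if administrative; if significant, IRB approval and, where applicable, regulatory approval. It could be included in the next amendment, with sites told in the meantime which devices are intended. No data collection, endpoint or analysis needs to change.
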